This is a Double-blinded randomized placebo-controlled trial based at Eastern Virginia Medical School. Subjects who are identified in clinic having menorrhagia or abnormal Uterine bleeding (AUB) due to uterine fibroids and meet inclusion criteria based on the ultrasound (US) or Magnetic Resonance Imaging (MRI), aged 18-45 undergoing laparoscopic or Robotic assisted myomectomies. These subjects will be then approached for consent during their pre-op visit 1-2 weeks prior to their surgery. The setting for consent will be in a patient consultation room. A total of 50 women in each arm of the study with symptomatic fibroids meeting any of the following criteria will be included in the study:

1) At least one fibroid greater than or equal to 6 cm (7)

2) Any intramural or broad ligament fibroid greater than or equal to 4 cm (7)

3) At least 3 total fibroids based on preoperative imaging. (8)

Randomization will be performed using an automated randomization website (9)(Supplement 1)

Patients will be randomized to receive a single IV bolus injection of TXA 30mg/kg in 50ml of normal saline (intervention group) versus an IV bolus injection of normal saline of equivalent volume (placebo group) 15 minutes prior to initial surgical incision. This dosage will not be adjusted for patients with renal insufficiency as they will be excluded from the study. Preparation of the medications will be performed by anesthesia who have both medication and normal saline available to them on short notice. No prior preparation by pharmacy will be required. Tranexamic acid is readily available in a 10 ml vial, which does not need a pharmacist to prepare for administration. The vial is mixed with 50 ml of saline in the operating room. This is the same process that occurs outside of any study with any medication that is administered intra-operatively. This will in no way impact the patient's safety during the surgery, especially since it is administered 15 minutes prior to the start of the procedure.

The dosage of TXA is considered a high dose and has been shown in cardiothoracic, orthopedic and trauma surgery to be reduce blood loss and transfusion need in comparison to regular dosing. There has been no reported increases in TXA side effects with higher dosing of TXA in the literature. (10–12)

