Both surgeon and patient will be blinded to the treatment arm. This dosage has been used previously in both obstetric and gynecological procedures and is the same dose recommended by the WHO for preventing post-partum hemorrhage(13).

The surgery itself will be scheduled at either Sentara Norfolk General, Sentara Leigh hospital, and Sentara Princess Anne hospital. These are the three sites that the investigators already perform Minimally invasive myomectomies.

An envelope will be given to the anesthesiologist prior to the procedure informing whether they are to receives TXA or the placebo. Blood loss will be estimated by the surgeon performing the procedure. Hemoglobin and hematocrit will be obtained 24 hours post procedure. The patient will be assessed for reported side effects from the medication given will be assessed by a questionnaire that will be given at their post-op appointment at the 2 week and 6-week mark. During these two visits a physical exam is performed, checking incision sites, and patient symptoms, all of which are standard of care for any minimally invasive procedure. The patients will be seen at the EVMS outpatient clinic for Gynecology or

depending with the physician who performed the surgery. Data will be collected from both Allscripts and EPIC charts.

Primary Outcomes measured

- 1. Estimated blood loss at time of procedure completion; using volume of cannister and weight of lap sponges
- 2. Calculated Blood loss, using pre-operative hematocrit, postoperative hematocrit and estimated blood volume x Body Mass Index
- 3. Number of blood products received during admission that is directly due to blood loss at time of procedure

Secondary outcomes

- 1. Duration of surgery
- 2. Length of hospital stay
- 3. Number of fibroids removed
- 4. Fibroid types 0-8
- 5. Total Weight of fibroids removed
- 6. Pain index on post-operative day 1, and 2-week post-operative visit
- 7. Post-operative complications
 - a. Readmission
 - b. Postoperative fever
 - c. Postoperative infection
- 8. Reported mild side effects of medication (Supplement 2)
 - a. Diarrhea
 - b. Nausea
 - c. Headache
- 9. Reported Serious Side effects of medication (Supplement 2)
 - a. Shortness of breath
 - b. Deep vein thrombosis
 - c. Pulmonary Embolism

Patient data will be collected in a data collection tool with the subjects de-identified.

A subject identifying tool will also be sued to identify the subject with their EPIC and Allscripts MRN.

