Both epic and Allscripts will be used to collect patient data

Inclusion Criteria

- 1. Female
- 2. Age 18-45

- 3. Undergoing laparoscopic myomectomy
- 4. At least one fibroid greater than or equal to 6 cm
- 5. Any intramural or broad ligament fibroid greater than or equal to 4 cm
- 6. At least 3 total fibroids based on preoperative imaging

Exclusion Criteria

- 1. Severe existing medical complications involving the heart, liver, or kidney
- 2. Moderate to severe renal impairment (serum creatinine > 1.4)
- 3. Blood clotting abnormalities
- 4. Age <18
- 5. Known Allergies to tranexamic acid
- 6. Known Contraindications to Minimally invasive myomectomies
- 7. If you are pregnant
- 8. History of a prior blood clot in the lung, arm, or leg, known as pulmonary embolism or deep vein thrombosis
- 9. Any active blood clots, clotting disease, pulmonary embolism, cerebral thrombosis, estrogen use, renal impairment, elevated creatinine level
- 10. History of a stroke or mini-strokes

11. History of prior seizures

- 12. Concurrent oral contraceptive use
- 13. Contraindications to receiving Tranexamic acid
 - i. In patients with acquired defective color vision, since this prohibits measuring one endpoint that should be followed as a measure of toxicity
 - ii. In patients with subarachnoid hemorrhage. Anecdotal experience indicates that cerebral edema and cerebral infarction may be caused by tranexamic acid in such patients.
 - iii. In patients with active intravascular clotting.
 - iv. In patients with hypersensitivity to tranexamic acid or any of the ingredients

Statistical Analysis

Descriptive statistics will be calculated. Continuous variables will be compared with t-test and categorical variables will be compared with Chi-square. P-values of less than 0.05 will be considered significant. A logistic regression will be performed to calculated the adjusted odds ratio.

Sample size calculation was set at 90 % power to detect a 150 ml difference in blood loss, with a significant level of 5 % and a one-sided alpha of 0.05 and beta (β)-set at 0.1.

The sample size was calculated using the formula below.

N=2 Σ^{2} (z α +Z1/2 β)²/r²

Substituting with figures:

 $N=2\times135\times135(1.96+1.282)^2/150^2=17$ patients in each group.(14) However, we wish to include 50 patients on each arm to try to increase the chances of identifying any side effects associated with the procedure

Risks of Study

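### Cheap improvement, not an error: no adjusted difference in mL is planned for the blood-loss primaries, although preoperative imaging of fibroid size and number is at hand

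*Combined protocol and SAP*

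**What the plan says.** The Statistical Analysis section gives two general rules: "Continuous variables will be compared with t-test and categorical variables will be compared with Chi-square". It then adds one adjusted analysis: "A logistic regression will be performed to calculated the adjusted odds ratio". It names no outcome or covariates for that regression, and no linear model appears anywhere in the document.

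The first two items under Primary Outcomes are estimated and calculated blood loss, both continuous. The trial is sized on a mean difference in mL: "Sample size calculation was set at 90 % power to detect a 150 ml difference in blood loss". The calculation gives 17 per group. The plan enrols 50 per arm, and the stated reason is "to try to increase the chances of identifying any side effects", not precision for blood loss.

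Study Design bases eligibility on ultrasound or MRI findings of fibroid size, location and number, and admits women "meeting any of the following criteria will be included in the study". The Inclusion Criteria list the same three fibroid criteria as separate items without saying that any one is enough.

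**The concern.** If one of three fibroid criteria is enough, women in the same arm can differ widely in fibroid burden. If burden seen on imaging predicts blood loss, that variation goes into the error term of the t-test, where a linear model would remove it. The imaging precedes treatment, so adjusting for it is legitimate and needs no extra patients.

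The planned logistic regression cannot do this job. Whatever its outcome turns out to be, it returns an odds ratio, not an adjusted mean difference with an interval in mL. At stake is the width of the interval around the main result, and power for effects smaller than the design target. The validity of the comparison is not at stake.

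**Working it through.** **Inputs from the Statistical Analysis section.** SD 135 mL, target difference 150 mL, z values 1.96 and 1.282, 50 per arm. I use two-sided 0.05, because 1.96 is the value in the plan's formula.

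**Inputs assumed.** R², the share of blood-loss variance explained by the two imaging covariates: 0 to 0.4. An effect of 60 mL to illustrate power. A normal outcome. No dropout.

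**1. The plan's own figure.** 2 × 135² × (1.96 + 1.282)² / 150² = 17.03, which matches the stated 17 per group.

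**2. t-test at 50 per arm.** SE = 135 × √(2/50) = 27.0 mL. The half-width is 1.984 × 27.0 = 53.6 mL. Its average is about 53.4 mL, because an estimated SD falls slightly below the true one on average (factor 1 − 1/(4 × 98) = 0.9974). Power from the noncentral t with 98 df is 59.5% at 60 mL, 95.6% at 100 mL and 99.98% at 150 mL.

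**3. Linear model: arm, largest diameter, fibroid count (96 df).** Two covariates inflate the SE by about √(1 + 2/95) = 1.0105. At R² = 0 the mean half-width is 1.985 × 27.0 × 1.0105 × 0.9974 = 54.0 mL. In general it is about 54.0 × √(1 − R²). The equivalent number per arm is 50 × (53.4 / adjusted half-width)².

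| Assumed R² | Mean half-width (mL) | Equivalent n per arm for a t-test |
|---|---|---|
| t-test | 53.4 | 50 |
| 0 | 54.0 | 49 |
| 0.1 | 51.2 | 54 |
| 0.2 | 48.3 | 61 |
| 0.3 | 45.2 | 70 |
| 0.4 | 41.8 | 82 |

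Break-even: 1 − (53.4/54.0)² = 0.022, so R² of about 0.02. A simulation of this model (20,000 replicates per R² value) gave the same half-widths.

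**4. Power at the assumed 60 mL.** With SE = 27.0 × 1.0105 × √(1 − R²), that is 25.9, 24.4, 22.8 and 21.1 mL at R² 0.1 to 0.4, simulated power is about 63%, 68%, 74% and 80%, against 59.5% for the t-test.

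**5. Adding hospital.** Surgery takes place at "Sentara Norfolk General, Sentara Leigh hospital, and Sentara Princess Anne hospital". With a three-hospital term the half-width at R² = 0 is 54.5 mL, and break-even moves to 1 − (53.4/54.5)² = 0.04. The hospital term therefore accounts for about half of the 1.1 mL loss.

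**6. If the SD is larger than planned.** At an assumed SD of 270 mL (twice the plan's value), SE = 54.0 mL. Normal-approximation power for 150 mL is 79.3% unadjusted, 83.4% at R² = 0.1 and 91.3% at R² = 0.3. These adjusted figures leave out the small covariate cost in step 3.

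**The case against.** The strongest reply is that nothing needs repair. A t-test in a randomised trial is valid, and power at the plan's own target is essentially complete. The power gain shows only at an effect that the documents do not target, and the precision gain depends on an R² that they do not give. At R² = 0.1 it is about 2 mL. All of this stands, and it is why the point is an improvement and not an error. It does not remove the gain, since a narrower interval is useful at any power and the possible loss is about 0.6 mL.

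Three further limits also stand:

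- The SD of 135 is given for blood loss in general, and the study cited beside it is, by its title, a trial in open myomectomy. It cannot be tied to calculated blood loss, whose definition reads "Calculated Blood loss, using pre-operative hematocrit, postoperative hematocrit and estimated blood volume x Body Mass Index", so the mL figures apply to estimated blood loss only.
- Imaging may be ultrasound or MRI, so diameter and count may not be measured alike. If all the listed fibroid criteria were required, burden would also vary less. Either would lower R².
- No passage shows that hospital predicts blood loss, so that term is optional.

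A reader might infer that the plan makes no use of fibroid data in any blood-loss analysis. The documents do not support this. The logistic model is unspecified, and it could take dichotomised blood loss as its outcome with fibroid burden as a covariate. What is certain is narrower: no adjusted difference in mL is planned.

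**Conclusion.** The point holds as a low-cost improvement. The blood-loss primaries get an unadjusted t-test, and the one adjusted analysis is on a scale that cannot yield a difference in mL. For estimated blood loss at SD 135 and 50 per arm, adjusting for two imaging covariates would narrow the interval by about 4% at R² = 0.1 (51.2/53.4 = 0.96) and about 22% at R² = 0.4 (41.8/53.4 = 0.78). The size rests on the assumed R², the plan's SD and a roughly normal outcome.

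A reader might infer that the trial is underpowered or its primary test unsound. Under the plan's own inputs neither is so. Adjustment would matter for power at 150 mL only if the SD were well above 135.

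Three matters are separate and add no weight here: the unnamed outcome and covariates of the logistic regression, the wording "with a significant level of 5 % and a one-sided alpha of 0.05" beside a formula that uses 1.96, and the body mass index term in the calculated-loss formula.

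**What to change.** In the Statistical Analysis section, add text such as: *Estimated blood loss will be analysed by linear regression on treatment arm, adjusted for largest fibroid diameter and fibroid count on preoperative imaging. The adjusted mean difference with its 95% confidence interval is the main result; the t-test is a sensitivity analysis.* Apply the same model to calculated blood loss once its formula and unit are settled. Hospital may be added, at the small cost shown above.

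Do not adjust for the number or weight of fibroids removed. Both are recorded after randomisation.

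The cost is one or two sentences, fixed before unblinding. Diameter and count must be recorded for every patient from the eligibility imaging. The fields of the data collection tool are not in the supplied text, so two may have to be added. State how a missing covariate value will be filled in without reference to arm or outcome, so that no randomised patient drops out of the model. The statistical downside is the loss of about 0.6 mL in half-width if the covariates predict nothing.

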A Randomized Control Trial Investigating the impact of High dose Prophylactic Tranexamic acid on blood loss at the time of minimally invasive myomectomy – Protocol

Proposed Research Study:

A Randomized Control Trial Investigating the impact of High dose Prophylactic Tranexamic acid on blood loss at the time of minimally invasive myomectomy

Investigators:

[name] [name] MD [name] [name] MD [name], PhD [name] [name] MD

Specific aim:

- 1. To compare the volume of blood loss in patients undergoing minimal invasive myomectomies who received prophylactic tranexamic acid vs placebo
- 2. To compare the number of blood products received during/post procedure in patients received tranexamic acid prophylactically vs placebo

This will be conducted as a double blinded randomized control trial. Data will be collected over a 3 year period with the goal of recruiting 50 patients per arm

Background and Significance

In minimal invasive gynecologic surgeries, operative blood loss is a common complication that affects postoperative morbidity and recovery (1). Antifibrinolytic drugs are well established in the management of surgical and traumatic bleeding(1–3). Tranexamic acid (TXA) is a synthetic lysine derivative that binds to plasminogen and inhibits the enzyme from breaking down fibrin deposits. In a recent Cochrane review last updated in 2015 that investigated the use of TXA in general surgery, TXA was found to reduce intraoperative and postoperative blood loss by 414 mL (95% confidence interval [CI] –525 to –303 mL) in comparison to placebo(4). In another Cochrane review 16 trials involving benign obstetrics and gynecologic were included. 14 studies involved women undergoing elective Cesarean deliveries and 2 studies involved women having abdominal myomectomy. No studies involving hysterectomy were identified and no studies involving minimal invasive myomectomies were identified(1)(5). Only recently, the first Randomized controlled double blind study was completed at George Washington University (6).

The results of this study have yet to be published. We hope to attempt to show the efficacy of prophylactic TXA use in minimal invasive myomectomies in reducing blood loss.

Study Design

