Cost of tranexamic acid will be covered as medications given during surgery; It is covered by insurance for gynecologic surgery because it is considered a primary method of hemostasis for surgery. This medication is used routinely in myomectomies, and there has been no issue covering the cost of the medication as part of the surgery outside of this study. Since anesthesia is administrating the medication and will be the only person not blinded to the study, they will also bill for the medication. This is usually how the medication is billed under normal circumstances.

Since there is no current funding for this study, the patient will be informed of the cost of the medication and they can refuse to participate if they do not want to pay for such medication.

The placebo will be normal saline that will be administered by anesthesia. It is not considered an additional cost to the surgery because of its normal use during any procedure

References

- 7. Parker WH. Uterine myomas: management. Fertil Steril [Internet]. 2007 Aug 1;88(2):255–71. Available from: https://doi.org/10.1016/j.fertnstert.2007.06.044
- 8. Lam S-J, Best S, Kumar S. The impact of fibroid characteristics on pregnancy outcome. Am J Obstet Gynecol. 2014 Oct;211(4):395.e1-5.

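### Blood products are a primary outcome, but the plan sets no common transfusion trigger and does not keep the unblinded anesthesiologist out of the decision

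*Combined protocol and SAP*

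**What the plan says.** All references are to the combined protocol and SAP.

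- **The outcome.** Specific aim 2 is "To compare the number of blood products received during/post procedure in patients received tranexamic acid prophylactically vs placebo". Primary outcome 3 begins "Number of blood products received during admission" and is limited to products attributable to operative bleeding. No one is named to make that attribution.
- **Who is blinded.** Study Design: "Both surgeon and patient will be blinded to the treatment arm".
- **Who is not.** Study Design: "An envelope will be given to the anesthesiologist prior to the procedure informing whether they are to receives TXA or the placebo". The same section says "Preparation of the medications will be performed by anesthesia who have both medication and normal saline available to them on short notice". The Budget section confirms the position: "Since anesthesia is administrating the medication and will be the only person not blinded to the study".
- **The other blood-loss outcomes.** For primary outcome 1, "Blood loss will be estimated by the surgeon performing the procedure". Primary outcome 2 is "Calculated Blood loss, using pre-operative hematocrit, postoperative hematocrit" combined with estimated blood volume and body mass index.
- **What is absent.** No section gives a hemoglobin, hematocrit, hemodynamic or blood-loss threshold for transfusion. None says who decides, and none keeps the anesthesiologist out of the decision. Surgery takes place at three hospitals, with no rule common to them.

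**The concern.** A product count depends on how much the patient bled and also on when someone chose to transfuse. If that choice is open to a clinician who knows the arm, the second part can differ between arms even when bleeding does not. A clinician who knows that TXA was given may hold off, and one who knows that saline was given may act sooner. Part of a difference in outcome 3 would then be a difference in practice, most plausibly flattering the drug.

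The other primary outcomes help only partly. The blinded surgeon's blood loss is a fair cross-check. But if blood loss and products both favour TXA, it cannot show how much of the product difference came from practice. Calculated blood loss is a weaker check, because a transfusion raises the postoperative hematocrit on which it depends.

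**Working it through.** **The plan's own figure.** The only calculation in the plan concerns blood loss: 2 × 135² × (1.96 + 1.282)² / 150² = 17.03, stated as 17 per group, with 50 per arm planned. It reproduces, but it says nothing about transfusion. The plan gives no figure for outcome 3.

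**Which products are exposed.** The Budget section makes anesthesia the only unblinded party, so the ward team is taken to be blinded. Only intraoperative products are then directly exposed to knowledge of the arm. Surgeon-estimated blood loss is not exposed in the same way.

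**Illustration of size.** Only the 50 per arm and the choice of tests (t-test for continuous variables, chi-square for categorical) come from the plan. The rest are assumptions:

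- no drug effect, and a two-sided 0.05 level;
- a transfusion rate p of 2% to 20%;
- half of transfusions are intraoperative, and 30% or 50% of those are averted in the TXA arm only, so the averted share is f = 0.5 × 0.30 = 0.15 or 0.5 × 0.50 = 0.25 of all TXA-arm transfusions;
- averted products are not made up later in the admission;
- products per transfused patient are 1 + Poisson(1), mean 2.

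The placebo rate is p and the TXA rate is p(1 − f). At p = 0.10 the expected number transfused is 50 × 0.10 = 5 on placebo. On TXA it is 50 × 0.10 × 0.85 = 4.25 or 50 × 0.10 × 0.75 = 3.75.

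False-positive rates follow. The t-test on counts uses 200,000 simulated trials per case, with Monte Carlo error of about 0.1 point or less. The chi-square on any transfusion is exact binomial.

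| Transfusion rate | Test | f = 0 | f = 0.15 | f = 0.25 |
|---|---|---|---|---|
| 5% | t-test | 2.9% | 2.9% | 3.1% |
| 5% | chi-square, uncorrected | 4.3% | 4.5% | 4.9% |
| 5% | chi-square, corrected | 0.7% | 0.7% | 0.8% |
| 10% | t-test | 4.5% | 5.0% | 6.1% |
| 10% | chi-square, uncorrected | 5.1% | 5.6% | 6.9% |
| 10% | chi-square, corrected | 1.8% | 2.0% | 2.6% |
| 20% | t-test | 4.8% | 6.3% | 8.8% |
| 20% | chi-square, uncorrected | 5.2% | 7.1% | 10.6% |
| 20% | chi-square, corrected | 2.8% | 3.9% | 6.0% |

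At rates of 2% and 3% the t-test rejects in 0.4% and 1.1-1.2% of trials, and the uncorrected chi-square in at most 1.3% and 2.8%. The shift makes no practical difference there.

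**Effect of make-up transfusion.** If a share m of the averted transfusions is given later by blinded staff, f becomes f(1 − m). With m = 0.5, the larger case falls to 0.25 × 0.5 = 0.125, below the 0.15 column. The table is therefore the least favourable end for its stated shifts.

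**The case against.** The strongest reply has four parts.

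1. **Waiting is not withholding.** The outcome covers the whole admission and hemoglobin is measured at 24 hours. A patient left anemic by intraoperative restraint can be transfused later by blinded staff, and that product still counts. This stands. It is why the figures assume no make-up and would shrink with it.
2. **The mechanism is inferred.** The documents do not say that anesthesia influences transfusion or that knowing the arm alters the choice. This stands too, but they do not exclude either, and the plan leaves the opening unguarded.
3. **The direction is not certain.** Risks of Study notes that TXA is on hand at all the hospitals for heavy intraoperative bleeding, and nothing bars its rescue use. Rescue TXA in placebo patients would narrow the difference. So favouring the drug is the most plausible direction, not an established one.
4. **The remedy is partial.** Emergency transfusions stay with the treating team. If most intraoperative transfusions are urgent, on which the documents are silent, the gain is mainly in record-keeping. That still matters, because the decider and the reason cannot be reliably reconstructed later.

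A reader might go further and infer that every transfusion decision, including those on the ward, could shift with the arm. The documents do not support that: they describe anesthesia as the only unblinded party. Nor do they support the inference that the blood-loss comparison is compromised in the same way, since a blinded surgeon makes that estimate.

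**Conclusion.** The point holds in a limited form. As written, the plan leaves a discretionary primary outcome open to a treating clinician who knows the arm, with no common trigger and no separation from the decision. A difference in intraoperative products could partly reflect that knowledge, most plausibly in favour of TXA.

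The size cannot be determined from the documents. Under the assumptions shown, the shift is negligible at transfusion rates of 5% or less. At a 10% rate it adds about 0.5 to 1.6 points to the t-test false-positive rate (5.0 − 4.5 and 6.1 − 4.5). At 20% it adds about 1.5 to 4.0 points (6.3 − 4.8 and 8.8 − 4.8). Later make-up transfusion would reduce all of these. Confidence is medium, because both steps of the mechanism are inferences. The change is worth making because it is cheap and the missing records cannot be recovered afterwards; the point does not invalidate the trial.

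**What to change.** Before the first patient:

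- Adopt one written transfusion trigger for both arms at all three hospitals, its content set by the clinical leads.
- Make the blinded surgeon, or the blinded ward team after surgery, responsible for non-emergency decisions to give or withhold blood.
- For each transfusion, record whether it was intraoperative or postoperative, who decided, the reason, whether it was an emergency, and the hemoglobin and estimated blood loss known at that time. Report these by arm.
- If the trigger includes a hemoglobin level, use the 24-hour value already planned to list, by arm, patients who met it but were not transfused.
- State in the report that anesthesia was not blinded and that emergency transfusions remain exposed.

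**Cost.** A short amendment and a few data fields for transfused patients, with no extra staff or tests and no change in sample size. The downsides are slightly less clinical discretion outside emergencies, the need for anesthesia at three hospitals to agree, and emergency transfusions left uncontrolled. Covering those would need someone outside the case to prepare a coded infusion, which the plan does not provide for and which is not asked for here.

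### A study-drug charge arises in the TXA arm only, which conflicts with the stated patient blind and puts the 2- and 6-week patient-reported outcomes at risk

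*Combined protocol and SAP*

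**What the plan says.** Study Design states: "Both surgeon and patient will be blinded to the treatment arm". Budget makes anesthesia the only unblinded party and assigns it the billing: "they will also bill for the medication". It adds: "This is usually how the medication is billed under normal circumstances". Of the saline placebo, the same section says: "It is not considered an additional cost to the surgery because of its normal use during any procedure". Because the study has no funding, "the patient will be informed of the cost of the medication and they can refuse to participate" if unwilling to pay.

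On data sources, Study Design says: "Data will be collected from both Allscripts and EPIC charts". It also says that the investigators already operate at the three sites. Risks of Study limits access to the stored data to co-investigators.

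On timing, the side-effect questionnaire is given at the 2- and 6-week visits. Pain is recorded on post-operative day 1 and at 2 weeks. Estimated blood loss is taken at the end of the procedure, and post-operative hematocrit at 24 hours.

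The documents describe no masked or equal charge, no neutral medication entry, and no abstractor kept apart from the treatment record.

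**The concern.** The billing rule works against the blinding rule. A patient in the TXA arm generates a charge for the study drug, and a patient in the placebo arm does not. Each patient has been told in advance that TXA carries a cost, so she knows what the charge would mean.

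The outcomes exposed to this are those collected after she goes home. The mild side effects listed (diarrhea, nausea, headache) are self-reported and open to expectation, and so is 2-week pain. Side effects are not a minor part of this design, since Statistical Analysis gives them as the reason for enrolling 50 per arm. A bias in their reporting could produce a drug effect that does not exist or hide one that does.

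The charts may offer a second route. If the study dose is entered in EPIC or Allscripts as any intra-operative drug would be, whoever abstracts outcomes, possibly a surgeon-investigator, could see the arm. That would matter when classifying complications and when deciding whether blood products are attributable to operative blood loss, which is part of the third primary outcome.

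**Working it through.** **1. The plan's own figure.** Statistical Analysis gives 17 per group: 2 × 135² × (1.96 + 1.282)² / 150² = 17.03. The figure reproduces. The remaining 50 − 17 = 33 patients per arm are there to help identify side effects, which are the outcomes at risk here.

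**2. The provisions side by side.**

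| Item | TXA arm | Placebo arm | Source |
|---|---|---|---|
| Charge for study treatment | Billed in the usual way | No added cost | Budget |
| Patient told the TXA cost beforehand | Yes | Yes | Budget |
| Patient meant to know her arm | No | No | Study Design |

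The first row differs by arm and can reach the patient. The second tells her how to read it. Together they conflict with the third.

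**3. Which outcomes come after a bill could arrive.**

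| Outcome | When | Exposed to billing? |
|---|---|---|
| Estimated blood loss | End of procedure | No |
| Hematocrit-based blood loss | 24-hour sample | No |
| Pain | Day 1 | No |
| Pain | 2 weeks | Possible |
| Side-effect questionnaire | 2 and 6 weeks | Possible |

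Attribution of blood products and classification of complications are exposed only through the chart route, and only if TXA is charted visibly.

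**4. Possible size.** The documents give no side-effect rate, no share of patients who would see a charge, and no effect of seeing it on reporting. All three are assumptions. Let *p* be the true rate in both arms, *u* the share of TXA patients who see the charge, and *m* the factor by which those patients over-report. Then:

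reported TXA rate = *p* × [1 + *u*(*m* − 1)]; reported placebo rate = *p*.

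The false-positive rate is the sum of Bin(x; 50, TXA rate) × Bin(y; 50, placebo rate) over all pairs (x, y) for which the Pearson chi-square without continuity correction exceeds 3.84.

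| *p* | *u* | *m* | Reported rates | False-positive rate |
|---|---|---|---|---|
| 20% | 0 | – | 20% vs 20% | 0.052 |
| 5% | 0.5 | 1.5 | 5% × 1.25 = 6.25% vs 5% | 0.052 |
| 20% | 0.5 | 1.5 | 20% × 1.25 = 25% vs 20% | 0.093 |
| 20% | 1 | 1.5 | 20% × 1.5 = 30% vs 20% | 0.212 |
| 20% | 1 | 2 | 20% × 2 = 40% vs 20% | 0.595 |

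The last row is a worst case and is not relied on. The plan does not say whether chi-square is continuity-corrected. With the correction, 0.093 becomes 0.059 and 0.212 becomes 0.155.

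**The case against.** The strongest reply is that a charge may never reach the patient in time, or in a readable form. Budget says of TXA: "It is covered by insurance for gynecologic surgery because it is considered a primary method of hemostasis for surgery". Nothing says when a bill or statement is sent or whether it itemises the drug. This stands as a limit on certainty. It does not remove the conflict, because the same section expects that some patients may have to pay and describes no masking.

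A reader might infer that a TXA charge tells the patient her arm. The documents do not support that. Risks of Study says TXA is available at all the facilities for excessive intra-operative bleeding, and nothing says a placebo patient could not receive it. A charge is strong evidence of arm, not proof.

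A reader might also infer that the surgeon's blind is lost because the drug is in the chart. No section says that the study dose is entered in EPIC or Allscripts, and the abstractor is not named. It is a reasonable inference, since preparation and billing follow ordinary practice and no masked entry is described, but the surgeon part stays conditional on it.

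Finally, both blood-loss measures are fixed before any plausible bill, and readmission, deep vein thrombosis and pulmonary embolism are less open to reporting bias than nausea or headache. Both points are right and confine the concern. With a 5% base rate the illustration stays close to nominal, so a large bias should not be presumed.

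**Conclusion.** The point holds within those limits. As written, Budget creates a one-arm charge that patients have been prepared to recognise, and this conflicts with the patient blind in Study Design. What is at risk is the side-effect questionnaire at 2 and 6 weeks and pain at 2 weeks, provided that a bill or statement showing the drug arrives first. Attribution of blood products and classification of complications are at risk only if the dose is visibly charted.

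A reader might infer that the main blood-loss comparison is compromised. Billing gives no ground for that.

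The size cannot be estimated from the documents. Under the assumptions shown, the uncorrected false-positive rate for one side-effect item runs from about 5% to 9% and 21%, against a nominal 5%. The change is worth making because it is cheap and because no analysis can restore a blind once it is lost.

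**What to change.** Amend Budget and Study Design to state three things:

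- **Charge.** The study-drug charge is arm-neutral: either the same *study medication* line in both arms, or a charge held until after the 6-week questionnaire.
- **Record.** The study dose is entered as *TXA or placebo, study number*. Anesthesia keeps the allocation, and it is available in an emergency.
- **Abstraction.** Outcomes are abstracted without opening the medication or billing record.

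The cost is coordination with billing and records staff; no patients or procedures are added. The documents do not say whether the hospital can hold or relabel a charge. If it cannot, the protocol should qualify its patient-blind claim for the 2- and 6-week outcomes. Asking patient and surgeon to guess the arm at the last visit is optional: it describes how well the blind held but does not protect it.
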